15.3 Statistical Hypotheses

In this population, ORR in first line treatment in locally advanced or metastatic non-clear cell RCC (nccRCC) is assumed to be 15%. Most published ORR prior to 2019 was at ~8%. However, the most recently reported data in Feb, 2019, on Keynote 427 cohort B nccRCC, a phase II study, was 24.8% Hence, the ORR in this study is estimated $\geq 35\%$, which is deemed a clinical meaningful improvement. Hence, the null and alternative hypotheses are set as follows:

$$H_0: \text{ORR} \leq 15\% \text{ versus } H_a: \text{ORR} \geq 35\%$$

15.4 Sample Size Determination

The Simon's Two-Stage optimal design was adopted to design the study with a one-sided type I error rate of 5% and targeting for 80% power. Approximately 34 efficacy evaluable subjects will be enrolled. During the 1st stage, 9 subjects will be enrolled and if there are ≥ 2 responders as assessed by ORR, the study will proceed to Stage 2 in which 25 new subjects will be enrolled; otherwise, the study will stop early for futility. In the final analysis of 34 efficacy evaluable subjects, ≥ 9 responders are required to claim preliminary efficacy of the treatment combination over historical control in the same patient population.

The actual alpha level was 0.047 and the actual power was 0.811. The early termination probability is estimated at 0.5995 if null is true and the average sample size is around 19.

15.5 Population for Analyses

- Safety Analysis set: refers to the set of participants who take at least one dose of the study interventions and will be used for safety analysis.
- Efficacy Analysis set: refers to the participants who take at least two cycles of the combined study interventions and have baseline and at least one tumor assessment after receiving treatments unless discontinued due to disease progression, death or toxicity. Subjects received less than 2 cycles of combination treatments will be replaced with additional participants. Efficacy analysis set will be used as the primary set for ORR and other efficacy endpoints.
- Per-Protocol Analysis set: refers to the participants who follows the protocol without major violation and have received at least 80% of the targeted dosage. This set will be used for sensitivity analyses of the efficacy endpoints.

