6.2 Definitions of Evaluability

All patients who receive any study treatment are evaluable for toxicity. Patients are evaluated from first receiving study treatment until a 30-day follow up after the conclusion of treatment or death.

All patients who have received at least one cycle of therapy and have their disease re-evaluated will be considered evaluable for response (exceptions will be those who exhibit objective disease progression prior to the end of Cycle 1 who will also be considered evaluable).

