12.1 Antitumor Effect – Immune-Related RECIST (iRECIST) Criteria

12.1.1 Definitions

Evaluable for Adverse Events. All patients will be evaluable for adverse event evaluation from the time of their first treatment.

Evaluable for Response. All patients who have received at least one cycle of therapy and have their disease re-evaluated will be considered evaluable for response (exceptions will be those who exhibit objective disease progression prior to the end of Cycle 1 who will also be considered evaluable). Patients on therapy for at least this period and who meet the other listed criteria will have their response classified according to the definitions set out below.

Response and progression will be evaluated in this study using the revised international criteria (RECIST version 1.1) proposed by the RECIST committee as well as the modified iRECIST guidelines. Investigators should note the different requirements for confirmatory scans as well as follow up for the two criteria.

Until radiographic progression based on RECIST 1.1, there is no distinct iRECIST assessment. In participants who show evidence of radiological PD by RECIST 1.1 the Investigator will decide whether to continue a participant on study treatment until repeat imaging 4 to 8 weeks later is obtained using iRECIST for participant management. This decision by the Investigator should be based on the participant's overall clinical condition.

Clinical stability is defined as the following:

- Absence of symptoms and signs indicating clinically significant progression of disease
- No decline in ECOG performance status
- No requirements for intensified management, including increased analgesia, radiation, or other palliative care

Any participant deemed clinically unstable should be discontinued from study treatment at site-assessed first radiologic evidence of PD and is not required to have repeat tumor imaging for confirmation of PD by iRECIST.

If the Investigator decides to continue treatment, the participant may continue to receive study treatment and the tumor assessment should be repeated 4 to 8 weeks later to confirm PD by iRECIST, per Investigator assessment.

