15.2 Endpoints

The primary endpoint is ORR, defined as the proportion of response-evaluable patients who have a best overall response (BOR) of either CR or PR, as graded by RECIST V1.1.

The secondary endpoints include:

- 1) Toxicity profiles and adverse events. The severity of AEs will be graded according to NCI Common Terminology Criteria for Adverse Events (CTCAE) v5.0.
- 2) Progression-Free Survival (PFS): defined as the time from date of first dose of study drugs to date of first documented disease progression or death to any cause or latest follow up, whichever occurs first.

If the disease recurrence/progression assessment involves more than one date, the earliest date will be used as the event date. A patient will be censored at the date of the last radiographic disease assessment indicating a lack of recurrence, if any of the following occurs before documented disease progression:

- Patient is alive and progression free at the time of analysis data cut-off.
- Disease progression or death occurs right after missing data for a scheduled radiographic disease assessment (including missing the assessment or assessment results in an in-evaluable status for overall response per RECIST 1.1).
- Patient receives non-protocol systemic anticancer treatment.
- Patients missing baseline disease assessment will be censored at date of receiving first drugs.
- For equivocal findings of progression (*e.g.*, very small and uncertain new lesions; cystic changes or necrosis in existing lesions), treatment may continue until the next scheduled assessment. If progression is confirmed at the next scheduled assessment, the date of progression should be the earlier date when progression was suspected.

- 3) Overall Survival (OS), defined as the time from the date of first dose of study drugs until date of death from any cause or latest follow up.

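### The primary ORR denominator is defined inconsistently, the replacement sentence in 15.5 omits the exception for progression, death and toxicity, and no all-treated ORR is planned

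*Combined protocol and SAP*

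**What the plan says.** Three wordings of the ORR population are in the document.

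- **Response-evaluable.** Section 15.2 defines the primary endpoint as "the proportion of response-evaluable patients who have a best overall response (BOR) of either CR or PR". It cites no definition. The only matching term is in 6.2, repeated in 12.1.1: "All patients who have received at least one cycle of therapy and have their disease re-evaluated will be considered evaluable for response". The sole exception is: "exceptions will be those who exhibit objective disease progression prior to the end of Cycle 1 who will also be considered evaluable".
- **Efficacy analysis set.** Section 15.5 requires two cycles of the combination, a baseline assessment and at least one later assessment, "unless discontinued due to disease progression, death or toxicity". It then states: "Efficacy analysis set will be used as the primary set for ORR and other efficacy endpoints". Section 15.6.2 repeats that choice, and 15.4 and 15.6.5 count in the same unit ("In the final analysis of 34 efficacy evaluable subjects").
- **Subjects.** The synopsis and 3.0 define ORR as a proportion of subjects with no evaluability condition. Section 2.6.1 describes 34 enrolled subjects.

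On replacement, the sentence after the efficacy-set definition reads: "Subjects received less than 2 cycles of combination treatments will be replaced with additional participants". It carries no exception.

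The safety set (at least one dose) is assigned to safety analysis only. The one other efficacy population is the per-protocol set (no major violation, at least 80% of targeted dosage), of which 15.5 says: "This set will be used for sensitivity analyses of the efficacy endpoints".

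**The concern.** The decision rules are 2 responders among the first 9 and 9 among 34, so the classification of one patient can decide the outcome. The membership of the 9 and the 34 should therefore be fixed without ambiguity before data are seen.

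There are two separate problems. First, the one-cycle and two-cycle definitions class some patients differently, in both directions. Second, the replacement sentence, followed as written, substitutes a new patient for one who progressed, died or stopped for toxicity in the first two cycles. Such patients are mostly non-responders, so replacing them would tend to raise ORR relative to everyone treated. No planned ORR analysis would show by how much.

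**Working it through.** **Definitions side by side**

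| Patient | 6.2 / 12.1.1 | 15.5 definition | 15.5 replacement sentence, read literally |
|---|---|---|---|
| Dies or stops for toxicity in cycle 1, no scan | out | in, if the exception covers the two-cycle condition | replaced |
| Objective progression before the end of cycle 1 | in | in, on the same condition | replaced |
| Withdraws after one cycle, has the end-of-treatment scan | in | out | replaced |
| Lost to follow-up in cycle 1, no scan | out | out | replaced |

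The grammar of 15.5 also leaves open whether the exception applies to both the two-cycle and the assessment conditions or only to the latter.

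**Timing.** Two 21-day cycles end at week 6, and the first scheduled on-treatment scan is at week 9 (Schedule of Activities). A patient who stops before two cycles will often have no documented response. This is an inference: the schedule includes an end-of-treatment scan, and 2.6.1 and 6.8 continue scans after early stopping, so some could still respond.

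**Planned design reproduced.** Inputs from 15.3 and 15.4: p0 = 0.15, p1 = 0.35, n1 = 9, n = 34, continue if at least 2 responders, reject if at least 9.

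P(reject | p) = Σ over x = 2 to 9 of b(x; 9, p) × P[Bin(25, p) ≥ 9 − x]

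- p = 0.15: 0.0474 (stated 0.047)
- p = 0.35: 0.8107 (stated 0.811)
- Early termination under the null: 0.5995; expected size 9 + 25 × (1 − 0.5995) = 19.0, as stated

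The design figures are correct. (The text of 15.6.5 stops at 2 or fewer responders, against its own table and 15.4. That is a separate matter; the rule used here is the one that reproduces the stated figures.)

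**Effect of replacement on type I error.** Assume that 15% is the rate in all treated patients, that a share d of them is replaced, and that those replaced respond at f times the overall rate. The evaluable-set rate is then

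p = 0.15 × (1 − f·d) / (1 − d).

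For one replacement in 35 treated, d = 1/35 = 0.0286:

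- f = 0: p = 0.15 / 0.9714 = 0.1544; P(reject) = 0.0554
- f = 0.5: p = 0.15 × 0.9857 / 0.9714 = 0.1522; P(reject) = 0.0513
- f = 1: p = 0.15; P(reject) = 0.0474

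Larger assumed shares give 0.0622 (f = 0) or 0.0545 (f = 0.5) at d = 5%, and 0.0818 or 0.0631 at d = 10%. If 15% is an evaluable-patient rate, the result is 0.0474 whatever d is.

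**Observed ORR at the success boundary.** 9/34 = 26.5%. Adding back 1, 2 or 4 replaced non-responders gives 9/35 = 25.7%, 9/36 = 25.0% or 9/38 = 23.7%.

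**Effect of keeping one early failure in stage 1.** Treat one of the 9 as a certain non-responder and let the others respond at the design rate. The chance of at least 2 responders goes from 0.4005 (9 patients) to 0.3428 (8 patients) at 15%, and from 0.8789 to 0.8309 at 35%. Overall power becomes Σ over x = 2 to 8 of b(x; 8, 0.35) × P[Bin(25, 0.35) ≥ 9 − x] = 0.756.

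**The case against.** The strongest reply is that the analysis text is clear. Sections 15.5 and 15.6.2 name the efficacy set as primary for ORR, and 15.4 and 15.6.5 count the same unit. Only 15.2 says response-evaluable, and it does not cite 6.2 or 12.1.1. A statistician would use the 15.5 set. The exception also stands immediately before the replacement sentence, so carrying it forward is the natural reading; the literal one makes 15.5 contradict itself. Replacement can further be read as added enrolment rather than deletion from the set.

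This lowers the weight of the point but does not remove it. The term in 15.2 has no other definition to rest on, the replacement sentence states no exception, and on the natural reading withdrawals, losses to follow-up and investigator removals (6.7) before two cycles still leave the denominator.

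Several stronger readings might be inferred and are not supported:

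- **That the trial's type I error exceeds 5%.** This needs 15% to be an all-treated rate, which 15.3 does not say; 15.4 sizes the trial in efficacy-evaluable subjects, so the other reading is at least as natural. It also needs a replacement rate, and none is given. The 4 of 30 (13%) in 2.5 are stops for adverse events at any time in a clear cell study, and 15.5's exception would keep toxicity stops.
- **That the per-protocol set is a subset of the efficacy set.** Section 15.5 does not define it so; it sets no two-cycle or scan requirement. It is a different selected set, and it is not designed to restore the replaced patients.
- **That the all-treated ORR could not be obtained.** The safety set is defined, and 12.1.3 classifies best response for all patients. The figure could be derived; it is simply not planned.

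**Conclusion.** The point stands as an inconsistency in the definition of the primary analysis population, together with a replacement rule that omits its exception and the absence of a planned all-treated ORR. It should be fixed. The sample size and the stated operating characteristics are not in dispute.

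The size is conditional. With 15% as an all-treated rate and one replacement in 35, type I error is between 5.1% and 5.5%, depending on whether the replaced patient responds at half the overall rate or not at all. With 15% as an evaluable-patient rate it remains 4.7%. The documents do not settle which applies or how many replacements to expect, so these figures illustrate sensitivity and are not an estimate of bias.

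**What to change.** 1. Make the 15.5 efficacy set the single primary ORR set, and align the synopsis, 2.6.1, 3.0, 6.2, 12.1.1, 15.2 and 15.6.2 with it.
2. State in 15.5 that patients who discontinue for progression, death or toxicity stay in the set, count as non-responders unless they have a qualifying response, and are not replaced.
3. Add a sensitivity ORR in the safety set, counting anyone without a documented qualifying response as a non-responder. Report the number replaced, with reasons.
4. State in 15.3 whether 15% and 35% refer to evaluable or to all treated patients.

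**Cost.** Wording in eight or nine places and one extra analysis, with no change to the 2/9 and 9/34 rules or to the target of 34. A slightly lower all-treated ORR may be reported beside the primary result. Item 2 is not free of consequence for power: 0.811 holds only if the 35% rate already averages over the early failures that are kept. If it does not, one such patient in stage 1 lowers power to about 0.76. Item 4 should therefore be settled together with item 2.

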PR	Non-PD/not all evaluated	No	PR	
SD	Non-PD/not all evaluated	No	SD	Documented at least once ≥ 4 weeks from baseline

Integration of target, non-target, and new lesions into response assessment

Target Lesions	Non-Target Lesions	New Lesions	Overall Response	Best Response For This Category Also Requires
Not all evaluated	Non-PD	No	NE	
PD	Any	Any	PD	
Any	PD	Any	PD	
Any	Any	Yes	PD	

Non target lesions ONLY

No Target	CR	No	CR	Normalization of tumor markers, tumor nodes <10 mm
No Target	Non-CR/non-PD	No	Non-CR/non-PD	
No Target	Not all evaluated	No	NE	
No Target	Unequivocal PD	Any	PD	
No Target	Any	Yes*	PD	

Note: Patients with a global deterioration of health status requiring discontinuation of treatment without objective evidence of disease progression at that time should be reported as "symptomatic deterioration." This is a reason for stopping therapy, but is NOT objective PD. Every effort should be made to document the objective progression even after discontinuation of treatment.

*Investigators should record all new lesions. If the new lesion is felt to be equivocal, treatment may be continued pending further assessments.

12.1.4 iRECIST Response Assessment

Overall response will also be assessed using iRECIST. Immunotherapeutics may result in infiltration of immune cells leading to transient increase in the size in malignant lesions, or undetectable lesions becoming detectable. The criteria are identical to those of RECIST 1.1 in many respects but have been adapted to account for instances where an increase in tumor burden, or the appearance of new lesions, does not reflect true tumor progression.

Key differences are described below. All responses defined using iRECIST criteria are designated with a prefix. iRECIST time-point and best overall responses will be recorded separately.

Confirming progression: Unlike RECIST 1.1, iRECIST requires the confirmation of progression and uses the terms iUPD (unconfirmed progression) and iCPD (confirmed progression). Confirmatory scans should be performed at least 4 weeks, but no longer than 8 weeks, after iUPD.

iCPD is confirmed if further increase in tumor burden, compared to the last assessment, is seen as evidenced by one or more of the following:

- Continued increase in tumor burden (from iUPD) where RECIST 1.1 definitions of progression had been met (from nadir) in target, non-target disease, or new lesions.

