15.6.5 Planned Interim Analysis

An interim analysis for futility will be performed based on the Simon's 2-stage optimal design when 9 efficacy evaluable patients are evaluable for ORR. The study will stop early if 2 or fewer responders are observed. If 3 or more responders are confirmed before the planned interim analysis and the safety profiles of both drugs are acceptable, the study will continue to Stage 2 and a normal interim analysis may be waived. There will be no enrollment gap for the interim analysis.

At the final analysis with 34 efficacy evaluable patients, the study will claim preliminary efficacy to warrant further study if 9 or more responders are observed.

	Threshold
Interim Analysis	Continue to enroll if ≥ 2 responders among the first 9 efficacy evaluable patients
Final Analysis	Reject H_0 if ≥ 9 responders among n=34 patients

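### PFS and OS are timed from first dose but analysed in the efficacy set, which leaves out treated patients who stop early for reasons other than progression, death or toxicity, although they are still followed

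*Combined protocol and SAP*

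**What the plan says.** Section 15.2 times both endpoints from first dose; for survival it reads "Overall Survival (OS), defined as the time from the date of first dose of study drugs until date of death from any cause". PFS has the same origin.

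Section 15.5 then fixes the population: "Efficacy analysis set will be used as the primary set for ORR and other efficacy endpoints". To belong, a patient needs two cycles of the combination, a baseline scan and at least one later scan, "unless discontinued due to disease progression, death or toxicity". The next sentence replaces anyone with fewer than two combination cycles and does not repeat the exception. Section 15.6.3 specifies Kaplan-Meier for PFS and OS without naming a set. The only other efficacy population, per-protocol, is narrower still (no major violation, at least 80% of target dose) and is for sensitivity analyses.

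The note to the response table in Section 12.1.3 says of symptomatic deterioration: "This is a reason for stopping therapy, but is NOT objective PD". Section 6.7 keeps patients who stop treatment for any reason in follow-up. Section 6.8 adds survival contact about every 12 weeks until death, and scans about every 9 weeks until progression or new anticancer therapy.

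**The concern.** The clock starts at first dose, but whether a patient counts is decided by what happens afterwards. For ORR, an evaluability requirement is a familiar choice. For OS it has no purpose: no scan is needed, and the date of death is collected anyway. If those who leave outside the exception do worse than those who stay, the curves sit too high. With 34 patients and no control arm, two or three such patients visibly move a landmark estimate. Section 3.0 presents OS as the final proof of benefit, and no planned analysis would show the shift, because the one sensitivity set excludes even more patients.

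**Working it through.** **1. The plan's own figures.** Inputs from Sections 15.3, 15.4 and the table in 15.6.5: p0 = 0.15, p1 = 0.35; "Continue to enroll if ≥ 2 responders among the first 9 efficacy evaluable patients"; success at 9 or more of 34. Formulas: early termination = P(X1 ≤ 1 | 9, p); rejection = Σ over x = 2 to 9 of b(9, x, p) · P(X2 ≥ 9 − x | 25, p).

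| Quantity | Stated | Recomputed |
|---|---|---|
| Alpha | 0.047 | 0.0474 |
| Power | 0.811 | 0.8107 |
| Early termination under H0 | 0.5995 | 0.5995 |
| Average N under H0 | about 19 | 9 + (1 − 0.5995) × 25 = 19.01 |

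These reproduce. They rest on ORR alone, so the population for PFS and OS does not touch them. The plan states no event count, sample size or power for PFS or OS, so there is no survival figure to reproduce.

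**2. Who is left out.** Reasons for stopping (Section 6.7 and the 12.1.3 note) against the exception in 15.5, for a patient who stops before two cycles or before a first scan:

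| Reason | Covered by the exception? | Outcome data |
|---|---|---|
| Progression, death, toxicity | Yes, on the natural reading | Kept |
| Symptomatic deterioration | Unclear | Followed to death |
| Investigator removal, noncompliance | No | Followed to death |
| Withdrawal of consent, loss to follow-up | No | Up to last contact |

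The last row is limited because Section 2.6.1 ends follow-up at withdrawal of consent, and Section 6.9 treats unreachable patients as withdrawn. Omitted deaths that are actually on record would therefore come mainly from the two middle rows.

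**3. Which curve is affected.**
- OS: every omitted patient with follow-up belongs in the risk set, and every death counts.
- PFS: Section 15.2 generally censors a patient without an event at the last scan. An early leaver who is never rescanned is effectively censored at time zero and adds nothing. Section 15.2 also censors a death that comes directly after a missed scheduled assessment. An unscanned leaver therefore matters only by dying before the first missed scan (scans are every 9 weeks). A leaver rescanned off treatment under Section 6.8 also matters if progression is documented.
- Section 15.2 censors patients without a baseline scan at first dose. That rule has almost nobody to act on if the analysis set requires a baseline scan.

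**4. Size.** Because leavers are replaced until 34 are evaluable, all treated = 34 + k. Let S be the landmark probability in all treated and s that of the k omitted, with complete follow-up to the landmark. The efficacy set then gives [S(34 + k) − k·s]/34, so

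inflation = k(S − s)/34.

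The documents give neither k nor s. With s = 0 (all omitted patients fail before the landmark):

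| k (assumed) | S = 60% | S = 80% |
|---|---|---|
| 0 | 0 | 0 |
| 2 | 0.60 × 2/34 = 3.5 points | 0.80 × 2/34 = 4.7 points |
| 3 | 0.60 × 3/34 = 5.3 points | 0.80 × 3/34 = 7.1 points |

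If the omitted patients have half the overall probability (s = S/2), the inflation halves, to between 1.8 and 3.5 points over the same range. If they do as well as the others (s = S), it is zero.

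**5. A ceiling for PFS.** Take exponential PFS in the 34 with median 8.1 months (the first-line sunitinib figure in Section 2.2), and three omitted patients who all have counted events before 3 months. Then 3-month PFS is 0.5^(3/8.1) = 77.4% in the efficacy set and 77.4 × 34/37 = 71.1% in all treated; the median falls from 8.1 to 7.1 months. Step 3 means the real PFS effect should be smaller, since some of those events would be censored.

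**The case against.** The strongest reply is that Section 15.5 already keeps the early exits that matter most. Its exception covers progression, death and toxicity, so events in the first weeks count. A reader might infer that PFS and OS are confined to patients who complete two cycles and have a scan, that the bias is a guarantee-time bias in which nobody can fail early, or that every failure in the first six weeks is removed. On the natural reading of the exception, the documents do not support any of these. They would come close to holding only if the replacement sentence, which repeats no exception, overrides it; the text does not settle that.

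Three further objections have force. First, the exception speaks of disease progression without the word objective, which Sections 6.2 and 12.1.1 do use, so symptomatic deterioration may be meant to fall inside it. That makes its status unclear; it does not show that such patients are kept. Second, leavers outside the exception include people who withdraw or do not comply for reasons unrelated to prognosis, so it is an assumption that they do worse. Third, PFS and OS are secondary and descriptive, with no test or decision rule, so the go/no-go decision is untouched.

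What remains is that deaths collected by design can be left out of the OS curve, with no planned analysis to show it.

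**Conclusion.** The point holds in a limited form. The efficacy set omits treated patients who stop before two combination cycles or a first post-baseline scan for reasons outside the exception, while PFS and OS run from first dose. The effect is mainly on OS and smaller on PFS. Its size cannot be derived from the documents: 3.5 to 7.1 points is a worst case for k = 2 to 3 (assumed) and S = 60 to 80%, with every omitted patient failing before the landmark. It shrinks as those patients do better and is zero if none are omitted. The direction is upward only if omitted patients do worse than the rest, which is plausible for symptomatic deterioration and unknown for the other reasons. If the replacement rule overrides the exception, early progressions and deaths would be lost as well and the problem would be larger.

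**What to change.** - Section 15.5: limit the efficacy set to the response endpoints (ORR, CBR, DCR). DOR, being defined only for responders, can follow ORR.
- Section 15.6.3: name the safety set (all patients with at least one dose) as primary for PFS and OS, and report efficacy-set results as sensitivity.
- Section 15.5: state whether the exception for progression, death and toxicity governs the replacement sentence, and whether symptomatic deterioration falls under it.
- Section 15.2: reconcile the PFS censoring rules for missing baseline and missed assessments with the all-treated population, including how a death without a post-baseline scan is counted.

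The cost is a few sentences in the plan. Follow-up of patients who stop is already required, and sample size, alpha, power and the ORR rule stay as they are. The downside is that PFS and OS may look slightly less favourable.
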